10.1. Definitions

Pretreatment Event Definition

A pretreatment event is any untoward medical occurrence in a patient or subject who has signed informed consent to participate in a study but before administration of any study medication; it does not necessarily have to have a causal relationship with study participation.

Adverse Event Definition

Adverse event (AE) means any untoward medical occurrence in a patient or subject administered a pharmaceutical product; the untoward medical occurrence does not necessarily have a causal relationship with this treatment. An AE can therefore be any unfavorable and unintended sign (including an abnormal laboratory finding), symptom, or disease temporally associated with the use of a medicinal (investigational) product whether or not it is related to the medicinal product. This includes any newly occurring event, or a previous condition that has increased in severity or frequency since the administration of study drug.

With the exception of grade 3-4 laboratory abnormalities, an abnormal laboratory value will not be assessed as an AE unless that value leads to discontinuation or delay in treatment, dose modification, therapeutic intervention, or is considered by the investigator to be a clinically significant change from baseline.

Serious Adverse Event Definition

- Serious AE (SAE) means any untoward medical occurrence that at any dose:
- Results in death.Is life-threatening (refers to an AE in which the patient was at risk of death at the time of the event. It does not refer to an event which hypothetically might have caused death if it were more severe).
- Requires inpatient hospitalization or prolongation of an existing hospitalization.
- Results in persistent or significant disability or incapacity. (Disability is defined as a substantial disruption of a person's ability to conduct normal life functions).
- Is a congenital anomaly/birth defect.
- Is a medically important event. This refers to an AE that may not result in death, be immediately life threatening, or require hospitalization, but may be considered serious when, based on appropriate medical judgment, may jeopardize the patient, require medical or surgical

intervention to prevent 1 of the outcomes listed above, or involves suspected transmission via a medicinal product of an infectious agent. Examples of such medical events include allergic bronchospasm requiring intensive treatment in an emergency room or at home, blood dyscrasias or convulsions that do not result in inpatient hospitalization, or the development of drug dependency or drug abuse; any organism, virus, or infectious particle (eg, prion protein transmitting Transmissible Spongiform Encephalopathy), pathogenic or nonpathogenic, is considered an infectious agent.

Clarification should be made between a serious AE (SAE) and an AE that is considered severe in intensity (Grade 3 or 4), because the terms serious and severe are NOT synonymous. The general term *severe* is often used to describe the intensity (severity) of a specific event; the event itself, however, may be of relatively minor medical significance (such as a Grade 3 headache). This is NOT the same as *serious*, which is based on patient/event outcome or action criteria described above, and is usually associated with events that pose a threat to a patient's life or ability to function. A severe AE (Grade 3 or 4) does not necessarily need to be considered serious. For example, a white blood cell count of 1000/mm³ to less than 2000 is considered Grade 3 (severe) but may not be considered serious. Seriousness (not intensity) serves as a guide for defining regulatory reporting obligations.

Related

An event is "related" if more likely than not it was caused by the study drug

Unexpected

An event is "unexpected" when its specificity, nature, severity or incidence is not accurately reflected in the consent form, protocol, or IB previously reviewed and approved by the IRB. Examples include lower rate of response to treatment or a side effect that is more severe than initially expected.

Study Period

The study period is defined as the period of time from start of study drug through the End of Treatment visit. Events occurring after enrollment but prior to the study period will be considered pretreatment events (see above).

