10.2. Monitoring, Recording and Reporting of AEs

[name]., is the principal investigator of this study; The University of Arkansas for Medical Sciences (UAMS) is the study sponsor. UAMS is responsible for reporting serious adverse events (SAEs) to any regulatory agency; the principal investigator is responsible for reporting to the IRB and other entities (see Section 10.4).

AEs may be spontaneously reported by the patient and/or in response to an open question from study personnel or revealed by observation, physical examination, or other diagnostic procedures. When possible, signs and symptoms indicating a common underlying pathology should be noted as one comprehensive event. All AEs occurring during the study period must be recorded. The clinical course of each event should be followed until resolution, stabilization, or until it has been determined that the study treatment or participation is not the cause. SAEs that are still ongoing at the end of the study period must be followed up for up to 30 days to determine the final outcome. Any SAE that occurs after the study period and is considered to be possibly related to the study treatment or study participation should be recorded and reported immediately to the Sponsor (UAMS).

All subjects will be monitored for AE's during the study. Assessments may include monitoring the patient's clinical symptoms; laboratory, pathological, radiological, or surgical findings; physical examination; or other appropriate tests and procedures.

Planned hospital admissions or surgical procedures for an illness or disease that existed before the patient was enrolled in the trial are not to be considered AEs unless the condition deteriorated in an

unexpected manner during the trial (e.g., surgery was performed earlier or later than planned). All SAEs should be monitored until they are resolved or are clearly determined to be due to a patient's stable or chronic condition or intercurrent illness(es).

AE's are to be reported in a routine fashion at scheduled times during the trial, such as with the annual continuing review to the IRB. Certain AEs must be reported in an expedited manner to allow for more timely monitoring of subject safety and care. The preporting of these events depends on the characteristics of the event:

- Seriousness (grading of event)
- Relatedness to study therapy
- Expectedness

Steps to Determine if the event requires expedited Reporting:

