10.3. Expedited Reporting of SAEs

Only adverse events meeting the UPIRTSO (Unanticipated Problem Involving Risks to Subjects or Others) will need to be reported to the UAMS IRB within the required 10 day period of being notified of the event. UPIRTSO requires that an unanticipated problem meet the following qualifications: a) unanticipated or unexpected; b) related to the research; and c) involves new or increased risk to the subject(s). All other adverse events should be recorded and reported to the UAMS IRB at continuing review.

The Sponsor (UAMS) will be promptly notified of all SAEs that are related to the study and unanticipated/unexpected. These SAEs will be reported to the Sponsor using the FDA Medwatch 3500A. UAMS will report events to FDA in accordance with 21CFR312.

All other SAEs will be reported to the Sponsor and FDA in the Annual Progress Report.

Deaths that are related to research will be reported to the Sponsor immediately upon Investigator notification. A death due to a terminal condition of the research participant would be considered anticipated and not related to the research and therefore not immediately reportable under this policy. The sponsor will report deaths to FDA in accordance with 21CFR312.

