10.4. Other Required Reporting

AEs which are serious must be reported to Millennium Pharmacovigilance (or designee) from the date the participant signs Informed Consent through 30 days after administration of the last dost of ixazomib. Any SAE that occurs at any time after completion of ixazomib treatment or after the study period that the principal-investigator and/or sub-investigator considers to be related to any study drug must be reported to Millennium Pharmacovigilance (or designee). In addition, new primary malignancies that occur during the follow-up periods must be reported, regardless of causality to study regimen, for a minimum of three years after the last dose of the investigational product, starting from the first dose of study drug. All new cases of primary malignancy must be reported to Millennium Pharmacovigilance (or designee). Regardless of expectedness or causality, all SAEs (including serious pretreatment events) must also be reported to Millennium Pharmacovigilance:

Fatal and Life Threatening SAEs within 24 hours but no later than 4 calendar days of the investigator's observation or awareness of the event

All other serious (non-fatal/non-life threatening) events within 4 calendar days of the investigator's observation or awareness of the event

See below for contact information for the reporting of SAEs to Millennium Pharmacovigilance.

The investigator must fax the SAE Form per the timelines above. A sample of an SAE Form will be provided.

The SAE report must include at minimum:

Event term(s)

Serious criteria

Intensity of the event(s): Principal- or sub-investigator's determination. Intensity for each SAE, including any lab abnormalities, will be determined by using the NCI CTCAE version specified in the protocol, as a guideline, whenever possible. The criteria are available online at http://ctep.cancer.gov/reporting/ctc.html.

Causality of the event(s): Principal- or sub-investigator's determination of the relationship of the event(s) to study drug administration.

Follow-up information on the SAE may be requested by Millennium.

Intensity for each SAE, including any lab abnormalities, will be determined by using the NCI CTCAE version 4.0, as a guideline, whenever possible. The criteria are available online at http://ctep.cancer.gov/reporting/ctc.html.

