Relationship to the study drugs for each SAE will be determined by the investigator or sub-investigator by responding yes or no to the question: Is there a reasonable possibility that the AE is associated with the study drug(s)?

The investigator must also provide Millennium Pharmacovigilance with a copy of all communications with applicable regulatory authorities related to the study product(s), as soon as possible but no later than 4 calendar days of such communication.

SAE and Pregnancy Reporting Contact Information

SAE and Pregnancy Reporting Contact Information

[contact] Email: [contact]

Suggested Reporting Form:

- SAE Report Form (if provided by Millennium)
- US FDA MedWatch 3500A: http://www.fda.gov/Safety/MedWatch/HowToReport/DownloadForms/default.htm
- Any other form deemed appropriate by the Sponsor and/or Principal Investigator

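### Section 10 uses unreconciled tests of drug-relatedness; if the 10.1 definition governs 10.3, an unexpected SAE rated possible during the study period is formally reported to the IND sponsor and FDA only in the annual report

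*Combined protocol and SAP*

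**What the plan says.** The only definition of a related event in section 10 is in 10.1: one where "more likely than not it was caused by the study drug".

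Section 10.2 names relatedness as one of the characteristics that decide expedited reporting. It then has the assessor choose among unrelated, unlikely, possible, probable and definite, and does not say which of these count as related. For later events it uses another test: "Any SAE that occurs after the study period and is considered to be possibly related to the study treatment" or to study participation must be reported to the sponsor at once.

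Section 10.3 sets the gate for prompt notice: "The Sponsor (UAMS) will be promptly notified of all SAEs that are related to the study and unanticipated/unexpected". The default for everything else is: "All other SAEs will be reported to the Sponsor and FDA in the Annual Progress Report".

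Section 10.4 has the investigator answer yes or no to whether there is a reasonable possibility of association with the drug. Under the same section every SAE, whatever its causality or expectedness, goes to the drug supplier's pharmacovigilance unit within 4 calendar days at the latest.

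The title page names the university as IND sponsor, and 10.2 makes it responsible for reporting SAEs to regulators. The supplier has neither role.

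**The concern.** Several tests of relatedness stand side by side with no rule for which one applies where. The strictest is the only one written as a definition, and the gate for prompt notice turns on the word it defines. An investigator could answer yes to the 10.4 question and, for the same event, conclude under 10.1 that it is not related and need not go promptly to the sponsor.

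What is at stake is how soon the party responsible for regulatory reporting formally learns of an unexpected serious event while other patients may still be on treatment. Two assessors following the protocol in good faith could also send identical events down different routes.

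**Working it through.** No arithmetic applies. The check sets the tests next to each other and then follows one event through them.

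| Place | Test | What it governs | Does *possible* meet it? |
|---|---|---|---|
| 10.1 | More likely than not caused by the drug | Sole definition of related | Not on the ordinary meaning; not stated |
| 10.2, steps for expedited reporting | Five categories | Whether expedited reporting is needed | No cut-point given |
| 10.2, SAEs after the study period | Possibly related | Immediate notice to the sponsor | Yes |
| 10.3 | Related to the study, and unexpected | Prompt notice to the sponsor | Depends on which definition is carried over |
| 10.4 | Reasonable possibility, yes or no | Causality entry for the supplier's SAE report | Yes on the ordinary meaning |

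Take an unexpected SAE that the investigator rates possible.

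1. **It occurs in the study period**, which 10.1 defines as first dose to the End of Treatment visit. *Possible* normally falls short of more likely than not, so under 10.1 the event is not related. It misses the prompt-notice gate in 10.3 and falls under the default, the Annual Progress Report to sponsor and FDA.
2. **It occurs after the End of Treatment visit.** The 10.2 rule for later events applies, and the sponsor must be told immediately. The rating is the same and the test is lower.
3. **The supplier's route.** During treatment, and up to 30 days after the last dose, the supplier is told within 4 calendar days whatever the rating. Nothing in 10.4 has the supplier pass the report to the IND sponsor or FDA.
4. **The 10.4 wording is used as the test in 10.3 instead.** The event in step 1 counts as related and is reported promptly.

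Steps 1 and 4 give different routes for the same event, and the protocol does not choose between them. Steps 1 and 2 show that an event in the study period faces a stricter test for prompt notice than a later one.

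Two other clauses in 10.3 turn on relatedness to the research: the 10-day report to the IRB and the immediate notice of deaths to the sponsor. The same uncertainty about *possible* carries into both.

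**The case against.** The strongest reply is that the consequence is inferred. No sentence says that *possible* means not related. The five categories appear under the steps for deciding on expedited reporting, so an assessor could fairly count *possible* as related. The gate in 10.3 speaks of relation to the study, while 10.1 speaks of causation by the drug. This stands: the route in step 1 is the natural reading and not an explicit rule, and the point is worded conditionally for that reason. The missing mapping is nevertheless the defect.

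It can also be said that the 10.4 question does not gate reporting during treatment, since the supplier receives all SAEs, and that different recipients may use different causality wording. That is correct. The conflict that matters is between 10.1, 10.2 and 10.3; the 10.4 question adds a further standard for the same judgement.

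Section 10.3 commits the sponsor to report to FDA under 21CFR312. What that requires cannot be checked from the documents, and the sponsor can act only on events it has been told about. The title page makes the obligations of investigator and sponsor joint, but 10.3 still prescribes a formal notification step with its own form.

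A reader might go further and infer any of the following, none of which the documents support:

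- *Every SAE rated possible waits for the annual report.* Section 10.2 requires immediate notice of such events after the study period.
- *A safety signal would go unseen for up to a year.* The investigator knows of the event and can modify dosing or withdraw patients under section 8.2, and the supplier is told within days. What is delayed is formal notice to the sponsor and FDA.
- *The trial's reported results would shift with the definition used.* Sections 3 and 9.1 plan no analysis of a related-event rate.
- *The overlapping wording on SAE follow-up and on the time limit for fatal events is part of the same fault.* Those clauses do not depend on relatedness.

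**Conclusion.** The point holds in a limited form. Section 10 states relatedness in ways that are not reconciled, and the five attribution categories have no cut-point. If the 10.1 definition is applied to the gate in 10.3, an unexpected SAE rated possible during the study period is formally reported to the IND sponsor and FDA only at the next Annual Progress Report. The supplier has the same event within 4 calendar days, and the same rating after the study period goes to the sponsor immediately.

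This rests on two assumptions: that *possible* lies below more likely than not, and that the 10.1 definition of related is the one meant in 10.3. Both are the ordinary reading; neither is written down. The documents give no expected number of such events and no date for the annual report, so the size can be stated only as this contrast in timing. It is more than a drafting preference, because following the stated definition delays formal notice to the party responsible for regulatory reporting. It should be corrected.

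**What to change.** Use one definition of related across 10.1 to 10.4, set at reasonable possibility. Suggested text for 10.1: *An event is related if there is a reasonable possibility that the study drug caused it. Ratings of possible, probable or definite count as related; unrelated and unlikely do not.*

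Apply that definition by cross-reference to the prompt-notice gate in 10.3, and have the IRB and death clauses there and the rule in 10.2 for SAEs after the study period point to it too. Copy to the sponsor, at the same time, the SAE form that already goes to the supplier. The default sentence in 10.3 would then need rewording, since the annual report would no longer be the sponsor's first notice of any SAE.

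The cost is wording and a copy of a form already completed. The downside is a few more prompt reports, some of which will turn out not to be caused by the drug.

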1.1.4.3. Pharmacokinetics and Drug Metabolism

Clinical IV and PO pharmacokinetic (PK) data show that ixazomib citrate (measured as the biologically active boronic acid form of ixazomib [MLN2238]) has multi-exponential disposition with a rapid initial phase that is largely over by 4 hours. Oral ixazomib is rapidly absorbed with a median time to first maximum plasma concentration (Tmax) of approximately 0.5 to 2.0 hours and terminal t1/2 after multiple dosing of approximately 5 to 7 days(14). Results of a population PK analysis (N = 137) show that there is no relationship between body surface area (BSA) or body weight and clearance (CL). Also, based on stochastic simulations for fixed dose, exposures are independent of the individual patient's BSA (15). Based on these data, a recommendation was made for fixed dosing in clinical trials. An absolute bioavailability of 67% was determined for ixazomib using the population PK analysis. Please refer to the current ixazomib IB and Safety Management Attachment (SMA) for information on the PK for IV doses of ixazomib.

Metabolism appears to be the major route of elimination for ixazomib, and urinary excretion of the parent drug is negligible (< 5% of dose). In vitro studies indicate that ixazomib is metabolized by multiple cytochrome P450s (CYPs) and non-CYP enzymes/proteins. The rank order of relative biotransformation activity of the 5 major human CYP isozymes was 3A4 (34.2%) > 1A2 (30.7%) > 2D6 (14.7%) > 2C9 (12.1%) > 2C19 (< 1%). Ixazomib is not an inhibitor of CYPs 1A2, 2C9, 2C19, 2D6, or 3A4 nor a time-dependent inhibitor of CYP3A4/5. The potential for ixazomib treatment to produce drug-drug interactions (DDIs) via CYP inhibition is inferred to be low. However, there may be a potential for DDIs with a concomitant strong CYP3A4 or CYP1A2 inhibitor or

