6. TREATMENT PLAN

All baseline assessments, labs, and bone marrow biopsies are to be completed within 35 days of enrollment. Radiological studies are to be completed within 60 days prior to enrollment.

Study drug (ixazomib 4.0 mg) will be given on Days 1, 8, 15, 22 of a 28- day cycle for a maximum of 6 cycles.

For a new cycle of treatment to begin, the patient must meet the following criteria:

- ANC must be $\geq 1,000/\text{mm}^3$.
- Platelet count must be \geq 75,000/mm³.
- All other non-hematologic toxicities should, at the investigator's discretion, generally be recovered to patient's baseline condition or Grade 1 or lower.

Dose modifications may be made based on toxicities during treatment described in detail in section 8.2.3. Treatment periods will be defined as 28-day cycles. Patients will be seen in clinic once per treatment cycle (Day 1) during their participation in the active treatment of the study. More frequent follow-up would be only as clinically indicated at the discretion of the treating physician.

Patients will be assessed for disease response and progression. Response will be assessed according to the IMWG criteria (see APPENDIX A) for all patients every 4 weeks for a maximum of 6 cycles (unless disease progression or unacceptable toxicity).

Patients will attend an End of Treatment (EOT) visit after completion of their 6 cycles (or at study discontinuation due to progressive disease, unacceptable toxicity, or other reason) and will continue to be followed for survival. Follow-up for survival after end of treatment will be limited to contact via telephone approximately annually to verify the patient's disposition. Verification of the patient's disposition may be performed by medical record review if the patient was seen in clinic at UAMS within 3 months of the scheduled follow-up interval.

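### AE recording closes at an End of Treatment visit with no minimum interval from the last dose, while Section 10.4 needs every SAE to 30 days after it and no contact is scheduled to find them

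*Combined protocol and SAP*

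**What the plan says.** Section 10.1 (Definitions) fixes the window: "The study period is defined as the period of time from start of study drug through the End of Treatment visit". Section 10.2 attaches the recording duty to it: "All AEs occurring during the study period must be recorded". For later events the same section narrows the duty by attribution: "Any SAE that occurs after the study period and is considered to be possibly related to the study treatment or study participation should be recorded", with immediate reporting to the IND sponsor. Its only 30-day clause concerns events already under way: "SAEs that are still ongoing at the end of the study period must be followed up for up to 30 days".

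Section 10.4 sets a different window for reports to the drug supplier. It starts at consent and runs "through 30 days after administration of the last dost of ixazomib". It covers all SAEs, with no filter on causality or expectedness.

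Sections 4.1 and 6 place the EOT visit after completion of 6 cycles, or at discontinuation. The termination text in Section 8.2.6 places the EOT procedures at the time of withdrawal. None of them gives a day, a visit window or a minimum interval from the last dose. EOT is the last column of the Section 7 schedule and holds the last toxicity evaluation. After it, Section 6 says that follow-up "will be limited to contact via telephone approximately annually to verify" the patient's disposition, with medical record review as an alternative.

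**The concern.** The same patient has two end dates and two causality filters. Suppose a patient has EOT a week after the last dose and an SAE judged unrelated on day 20. Section 10.2 does not ask the site to record it, yet Section 10.4 requires it to be reported.

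The practical difficulty is finding such events. The Section 10.4 deadlines, 24 hours to 4 calendar days, run from the investigator's awareness, and nothing scheduled between EOT and the annual contact creates awareness. SAEs will come to light only if the patient happens to return or someone calls. For new non-serious AEs in that interval there is no scheduled enquiry, and the Section 10.2 recording duty has ended.

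Section 9.1 makes every treated patient evaluable for toxicities and safety. With 20 patients, a few unseen events would change the reported rates noticeably. The interval is also pharmacologically relevant: Section 1.1.4.3 gives a "terminal t1/2 after multiple dosing of approximately 5 to 7 days".

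**Working it through.** The plan gives no figure to reproduce. The check is calendar arithmetic on its own schedule.

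**Inputs**
- Dosing on Days 1, 8, 15 and 22 of a 28-day cycle, at most 6 cycles (Sections 4.1 and 6).
- SAE window closing 30 days after the last dose (Section 10.4).
- Maximum delay of 3 weeks before treatment is discontinued (Section 8.2.3.1; Section 8.2.3.3 adds principal investigator discretion).
- Terminal half-life of 5 to 7 days (Section 1.1.4.3).
- Assumption: EOT on Day 29 of Cycle 6 for a completer, because no EOT window is stated.

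**Formula**

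Uncovered days = (last-dose day + 30) − EOT day, with a minimum of 0.

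**Completer, no delays**
- Last dose: 5 × 28 + 22 = day 162.
- The Section 10.4 window closes: 162 + 30 = day 192.
- EOT on Day 29 of Cycle 6: 5 × 28 + 29 = day 169. Uncovered: 192 − 169 = 23 days, or 23/30 = 77%.
- EOT on the last day of Cycle 6, day 168. Uncovered: 192 − 168 = 24 days, or 80%.

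**Early stop, counted within the last cycle**
- Stop after a full 3-week delay: last dose Day 22, next cycle due Day 29, delay exhausted on Day 29 + 21 = Day 50. Interval from last dose: 50 − 22 = 28 days. Uncovered: 30 − 28 = 2 days.
- EOT the day after a dose: 30 − 1 = 29 days uncovered.
- EOT on the day of the last dose: 30 − 0 = 30 days uncovered.

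**Next scheduled contact**

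It comes about 12 months after EOT. For a completer the window closes 23 days after EOT, so the contact falls roughly 11 months too late.

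**Exposure, for context only**

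Fraction of the terminal-phase level remaining = 2^(−t/half-life).
- At 7 days: 2^(−7/5) = 0.38 and 2^(−7/7) = 0.50.
- At 30 days: 2^(−30/5) = 0.016 and 2^(−30/7) = 0.051.

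Exposure therefore continues through much of the uncovered interval. This says nothing about how many events would be missed.

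**The case against.** The strongest reply is that safety reporting does not stop at EOT. That is correct. Possibly related SAEs after the study period must still be recorded and reported (10.2). Related SAEs are reportable to the supplier without time limit, and new primary malignancies for at least three years (10.4). Events present at EOT are not lost either: 10.2 follows each event's course to resolution or stabilization, or until study treatment and participation are ruled out as the cause, and follows the outcome of ongoing SAEs for up to 30 days. So a reader should not infer that all AE collection ends at EOT. What remains is new-onset events, and the continuing duties work only if the site hears of them.

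A reader might also infer that an unrelated SAE after EOT never reaches the IND sponsor. The documents do not support that. Section 10.3 sends all other SAEs to the sponsor and FDA in the Annual Progress Report, with no causality filter and no study-period limit, and 10.4 requires an SAE report from the site in any case. Section 10.3 likewise says that other adverse events should be recorded and reported to the IRB at continuing review. These are reporting routes, however. They set no collection window and schedule no contact, so they leave the conflict between 10.2 and 10.4 open and do not help the site find events.

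A third tempting inference is that the gap falls mainly on patients who stop for toxicity. That does not follow. The hold-and-re-evaluate route in Section 8.2.3 can put EOT about 28 days after the last dose, leaving about 2 days, while an ordinary completer loses about 23. The 29- and 30-day cases belong to abrupt stops.

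Finally, safety is neither an objective nor an endpoint, and a late EOT visit would close the gap for that patient. Both are true. The protocol does not require a late EOT, though, and Section 9.1 still treats patients as evaluable for toxicity.

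**Conclusion.** The point holds as a gap in ascertainment and a conflict between recording windows. Sections 10.1 and 10.2 end routine recording at a visit that is not tied to the last dose. Section 10.4 needs every SAE to 30 days after that dose, and no scheduled contact supports it.

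The 23-day figure for completers rests on the assumed Day 29 visit. The range for early stops, about 2 to 30 days, depends on the route by which treatment ends. Any bias in toxicity rates is towards too few events, but the documents give no basis for a size, and the half-life figures do not supply one. The point does not touch the primary osteocalcin analysis. It should be corrected because the remedy is small and the 10.4 duty cannot otherwise be met reliably.

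**What to change.** - **Section 10.1:** define the study period, for safety recording, as start of study drug through the later of the EOT visit and 30 days after the last dose. State that the exit osteocalcin, marrow and imaging assessments stay at the EOT visit.
- **Section 7:** add one row for a telephone AE/SAE contact at 30 days after the last dose, satisfied by an EOT visit held on or after that day. Mention the contact in Section 6, so that the sentence limiting later follow-up to an annual call no longer excludes it.
- **Section 10.2:** record all SAEs in that window whatever their attribution. The existing 30-day outcome follow-up is counted from the end of the study period and would move with the new definition, so say whether that is intended.
- **Sections 10.3 and 10.4:** align them with the same end date, and say which SAEs go to the sponsor promptly and which in the annual report.

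The cost is a protocol amendment, with FDA and IRB handling under Sections 12.2 and 12.5, and at most 20 telephone calls. It adds no clinic visit or procedure and changes no dose or treatment rule.
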